8.1.2 Sensitivity Analyses

8.1.2.1 Sensitivity Analysis for Handling of Missing Data

As a sensitivity analysis for handling of missing data, placebo multiple imputation and tipping point analysis on MNAR assumption will be performed using a pattern-mixture model with multiple imputation.

Multiple imputation analysis will be performed according to the following procedure. The number of imputations will be 100.

- 1) The Markov Chain Monte Carlo (MCMC) method will be used to impute intermittent missing data to produce a monotone missing data pattern.
- 2) The monotone regression method will be used to impute monotone missing data.
- 3) The same MMRM as that of the primary efficacy analysis will be used to analyze the multiple-imputed datasets.
- 4) The MIANALYZE procedure will be used to integrate the analysis results of the multiple-imputed datasets, and the estimate of the difference between the OPC-64005 20-mg group and the placebo group at Week 6 in the double-blind treatment period and its 95% CI and p-value will be determined.

In placebo multiple imputation, for discontinued subjects in each OPC-64005 group, MNAR will be assumed for missing data after discontinuation and an imputation model based on the placebo group will be used in imputation.

In tipping point analysis, for subjects in each OPC-64005 group who discontinued treatment for any of the following reasons, MNAR will be assumed for missing data after discontinuation.

- Withdrawal for any reason
- Withdrawal due to AEs, a lack of efficacy, or consent withdrawal
- Withdrawal due to AEs or a lack of efficacy

For subjects in each OPC-64005 group who discontinued treatment for reasons assumed as MNAR, the MAR assumption will be used to impute post-discontinuation missing data, add Δ (intergroup differences in MMRM of the primary efficacy analysis) \times k% to the imputed value, and increase k until a statistically significant conclusion is reversed ($p > 0.05$).

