The benefits of participating in the trial include the fact that depressive symptoms may improve, and that during the trial the subjects could receive more detailed tests and examinations by physicians than they could have with just general examinations. As of Oct 2019, no TRIs have been approved for the indication of depression/depressive symptoms in Japan or overseas.

3 Objectives and Endpoints

The objective of the trial is to compare the efficacy of OPC-64005 at 20 mg vs placebo and to assess the safety and pharmacokinetics (PK) of OPC-64005 at 10 and 20 mg in patients with MDD.

The primary endpoint is the mean change from baseline in Montgomery-Åsberg Depression Rating Scale (MADRS) total score at Week 6 of the double-blind treatment period in the OPC-64005 20-mg group compared with the placebo group.

The secondary endpoints are the MADRS response rate (proportion of subjects with ≥ 50% reduction from baseline in MADRS total score at Week 6 of the double-blind treatment period), MADRS remission rate (proportion of subjects with MADRS total score ≤ 10 and ≥ 50% reduction from baseline in MADRS total score at Week 6 of the double-blind treatment period), Clinical Global Impression – Improvement (CGI-I) improvement rate (proportion of subjects with CGI-I of 1 or 2 at Week 6 of the double-blind treatment period), mean change from baseline in Clinical Global Impression – Severity of Illness (CGI-S), mean change from baseline in the total score of 17 items of the Hamilton Rating Scale for Depression (HAM-D), mean change from baseline in Apathy Scale score, mean change from baseline in the total score of MADRS Self-assessment (MADRS-S), and mean change from baseline in MADRS anhedonia factor score for evaluation of the efficacy of OPC-64005 at 20 mg.

The safety and PK of OPC-64005 at 10 mg and 20 mg will also be assessed in patients with MDD.

Table 3-1 Trial Objectives and	d Endpoints					
Objectives	Endpoints					
Primary: To compare the efficacy of OPC-64005 at	Primary endpoint: Change from baseline in					
20 mg vs placebo administered orally as repeated	MADRS total score at Week 6 of the double-					
doses once daily for 6 weeks in patients with MDD	blind treatment period					

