In Trial 277-201-00001, on the other hand, the incidence of AEs that led to discontinuation of the trial in the OPC-64005 group was 23.4% (18/77 subjects) and higher than that in the placebo group (8.5%, 7/85 subjects). Most of these AEs occurred during the early stage of treatment initiation (during treatment at 20 mg). Therefore, in consideration of safety at an early stage of treatment, the starting dose in the present trial was set at 10 mg, which is lower than the starting dose of Trial 227-201-00001.

As of Oct 2019, there are no TRIs approved in Japan or overseas, and the safety profile is unknown. The 10-mg group was also included in the trial because evaluation of safety at the lower dose is beneficial when assessing the safety profile of OPC-64005.

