3.5.6 Apathy Scale

The Apathy Scale score will be the total score of Apathy Scale Items 1 through 14.

4 Sample Size

As no clinical trials of OPC-64005 in patients with MDD have been previously conducted, the target number of subjects was determined based on the results from another antidepressant clinical trial using MADRS score as the primary endpoint. In the phase 3 clinical trial of escitalopram conducted outside Japan, the mean change (\pm SE) from baseline in MADRS total score at the final time point of Week 8 (8 weeks after start of administration) determined using last observation carried forward analysis of covariance was -9.4 ± 0.9 in the placebo group ($n = 119$), -12.0 ± 0.9 in the citalopram 40-mg group ($n = 125$), -12.8 ± 0.8 in the escitalopram 10-mg group ($n = 118$), and -13.9 ± 0.8 in the escitalopram 20-mg group ($n = 123$). Referring to those results, in the present trial it is assumed that the difference between the OPC-64005 20-mg group and the placebo group in the change from baseline in MADRS total score at Week 6 of the double-blind treatment period will be -4 with a standard deviation of 11. To ensure a power of 80% in a two-sided test with a significance level of 0.05, 120 subjects each are

required for the OPC-64005 20-mg group and the placebo group. For the OPC-64005 10-mg group, the number of subjects was set at 30 without statistical consideration. The planned number of subjects to be randomized for the trial was therefore set at 270.

5 Statistical Analysis Datasets

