8.1.1 Primary Efficacy Analysis

For the primary analysis, an MMRM analysis will be performed using the OC dataset of the FAS.

The MMRM will include treatment group (OPC-64005 10-mg group, OPC-64005 20-mg group, and placebo group), time point (double-blind treatment period Weeks 1, 2, 3, 4, 5, and 6), and interaction between treatment group and time point as factors, and baseline and interaction between baseline and time point as covariates. An unstructured error variance-covariance structure will be assumed. For degree-of-freedom approximation, the

Kenward-Roger method will be used. The statistical comparison between the OPC-64005 20-mg group and the placebo group will be performed based on differences in the least square means at Week 6 of the double-blind treatment period between the 2 groups. If any problem occurs in the convergence status in the estimation of variance components, error variance-covariance structures of heterogeneous toeplitz, heterogeneous autoregressive of order 1, and heterogeneous compound symmetry will be applied in this order, and the first converged structure will be used in the primary analysis. If structures other than unstructured are selected, sandwich estimators of standard error will be used.

For each time point, the least square mean of each treatment group and the differences in the least square means between each OPC-64005 group and the placebo group, as well as the two-sided 95% confidence intervals (CIs), will be determined.

The time course of the least square means of the change from baseline in MADRS total score and standard errors will be plotted for each treatment group.

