8.1.3 Technical Computational Details for Primary Efficacy Analysis

The SAS code for the MIXED procedure to perform the primary efficacy MMRM analysis is shown below.

```
proc mixed;
  class treatment visit subjid;
  model change=treatment baseline visit treatment*visit baseline*visit / ddfm=kr;
  repeated visit /type=un subject=subjid;
  lsmeans treatment*visit / diff cl;
  ods output diffs=diffs lsmeans=lsmeans;
run;
```

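### Does the tipping-point rule move OPC-64005 dropouts the wrong way because the SAP gives Δ no sign?

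*SAP*

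**What the plan says.** SAP 8.1.2.1 plans two analyses under missing not at random for the primary endpoint, both by multiple imputation with 100 imputations: placebo multiple imputation and a tipping-point analysis. For the second it states: "For subjects in each OPC-64005 group who discontinued treatment for reasons assumed as MNAR, the MAR assumption will be used to impute post-discontinuation missing data". It then adds Δ × k% "to the imputed value, and increase k until a statistically significant conclusion is reversed", that is, until p exceeds 0.05. Δ is described only as the "intergroup differences in MMRM of the primary efficacy analysis". Step 4 of the procedure asks for the pooled Week 6 difference between 20 mg and placebo, with its 95% CI and p-value.

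Other places bear on the sign without settling it:

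- SAP 8.1.1 reports "differences in the least square means between each OPC-64005 group and the placebo group", which names the pair but gives no subtraction formula.
- The code in SAP 8.1.3 uses "lsmeans treatment*visit / diff cl". No control level is named and the treatment coding is not given, so the sign of the printed difference depends on the order of the class levels.
- SAP section 4 and Protocol 9.1 plan on a 20-mg versus placebo difference that "will be -4 with a standard deviation of 11".
- Protocol section 3 defines response as at least a 50% "reduction from baseline in MADRS total score at Week 6 of the double-blind treatment period", so a lower score is better.

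Protocol 9.3 leaves the details of the sensitivity analyses to the SAP.

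**The concern.** A tipping-point analysis asks how much worse than the missing-at-random prediction the drug dropouts would have to be before significance is lost. The shift must therefore raise their imputed MADRS change. The only between-group difference printed with a sign in either document is −4, and adding a negative Δ does the opposite: the larger k is, the better the drug dropouts look.

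Run that way, the search would not end, and the absence of a tipping point might be reported as robustness. If a programmer noticed and reversed the sign, the direction might seem to have been chosen after the data were seen. Dropout could be substantial and unequal. Protocol 4.3.2 reports adverse-event discontinuation of 23.4% (18/77) on drug against 8.5% (7/85) on placebo in the earlier AD/HD trial, although that was another population with a higher starting dose.

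**Working it through.** **Inputs.** Difference −4, SD 11, 120 per arm, two-sided 0.05, 80% power (SAP section 4, Protocol 9.1). The documents give no dropout rate for this trial. The shifted share d of the 20-mg arm is therefore an assumption, taken from 5% to 30%, with 23.4% borrowed from the AD/HD trial.

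**The plan's own figure.** The normal approximation gives n = 2 × (1.96 + 0.84)² × 11² / 4² ≈ 119 per arm. The t-test version gives 119.7, rounded up to 120. The stated 120 is reproduced.

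**The shift.** Write s = Δ × k/100, for an observed difference of −4. As an approximation to the pooled MMRM result:

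- estimate(k) = −4 + d × s
- SE(k) = √(2 × [11² + d(1 − d)s²/2] / 120)

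At k = 0, SE = √(242/120) = 1.42, z = −2.82 and p = 0.0049. At d = 23.4%:

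| k | Δ = −4: estimate, p | Δ = +4: estimate, p |
|---|---|---|
| 0% | −4.00, 0.0049 | −4.00, 0.0049 |
| 50% | −4.47, 0.0017 | −3.53, 0.013 |
| 100% | −4.94, 0.0005 | −3.06, 0.032 |
| 200% | −5.87, 0.0001 | −2.13, 0.143 |

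With Δ = −4 nothing tips up to k = 5000% for any d from 5% to 30%. With Δ = +4 the conclusion tips at these values of k:

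| d | 5% | 10% | 15% | 20% | 23.4% | 30% |
|---|---|---|---|---|---|---|
| tipping k | 545% | 288% | 196% | 149% | 128% | 100% |

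The effect of the sign is real and does not depend on d. The tipping values do depend on d, so they illustrate the rule and do not measure a defect.

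**Which reading does the text support?** There are three candidates for Δ.

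1. *Drug minus placebo, negative when the drug is better.* The estimate moves away from zero, p falls, and the stated end (p > 0.05) is not reached. At k = 5000% the shift is 4 × 50 = 200 points, on a scale whose maximum is 10 items × 6 = 60 (Protocol 8.1.1). If only three or fewer of 120 subjects were shifted, variance inflation alone would eventually push p over 0.05. At a difference of −4 that needs k of about 11,000% or more, a shift of at least 440 points, so it is no genuine tipping point.
2. *Placebo minus drug,* which is what the SAS code prints if placebo comes first in the class order. The rule works.
3. *The size of the difference,* a natural sense when differences between groups are mentioned without an order. The rule works.

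Only the first reading fails, and it fails because it contradicts the rule's own stopping condition.

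**The case for a change.** The strongest case for a change is that intent is not specification. SAP 8.1.2.1 fixes the number of imputations, the imputation methods and three sets of withdrawal reasons, yet leaves open the one symbol that sets the direction. Taken literally with the planning sign, the rule explores assumptions kinder to the drug than missing at random. The sign could be written down in a sentence before data lock at no cost.

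Part of this stands. The sign is not written, and the direction has to be inferred. The SAP also does not say which dose group's difference serves as Δ for the 10-mg dropouts, or whether the shift applies at visits before Week 6.

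The consequences do not stand:

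- **False robustness.** The procedure requires the estimate, CI and p-value. On the wrong sign the estimate moves further from zero and p falls at the first increment. Calling that robustness would mean ignoring the printed results.
- **Direction chosen after the data.** The stopping rule is already in the plan. For a significant result favouring the drug, it leaves one workable direction, so there is no discretion to exercise.
- **Dose group and earlier visits.** The reported comparison is 20 mg against placebo at Week 6. Once the imputed data are complete, the unstructured model with baseline-by-visit terms reduces at Week 6 to a three-arm analysis of covariance on baseline. A shift added to earlier visits after imputation then does not enter. The 10-mg shift acts only through the shared variance and baseline slope. At d = 23.4% and s = 4 it adds about 0.234 × 0.766 × 16 × 30/270 = 0.32 to a pooled variance of 121.

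**Conclusion.** No change to the plan follows. The SAP leaves a sign unwritten in a formula whose purpose and end point are both stated, and any analyst running a tipping-point search would add the shift that worsens drug dropouts. Writing the sign down would record the direction the stopping rule already implies and would alter no result.

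On the one reading that fails, the estimate goes from −4 to −4.94 and then −5.87 at k = 100% and 200%. On the readings that fit the rule, it tips at about 128%. Both figures assume 120 per arm, SD 11, an observed difference of −4 and 23.4% of the 20-mg arm shifted. The direction holds for every dropout share from 5% to 30%, but the tipping values do not carry over to other shares. The matter is confined to one supportive analysis in an exploratory Phase 2 trial. The primary MMRM, its single test, the sample size and the other missing-not-at-random analysis are unaffected.

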8.1.2.2 Sensitivity Analysis for Normality Assumption

As a sensitivity analysis for normality assumption, multiple imputation under the MAR assumption will be performed, and the Wilcoxon rank sum test will be used to compare the OPC-64005 20-mg group and the placebo group for each time point, and the Hodges-Lehmann estimator of the intergroup difference will be determined. A robust regression analysis with treatment group as a factor and baseline as a covariate will also be performed for each time point. If between-imputation variance is 0 because of the absence or paucity of missing data, analysis without multiple imputation will be performed.

8.1.3 Technical Computational Details for Primary Efficacy Analysis

The SAS code for the MIXED procedure to perform the primary efficacy MMRM analysis is shown below.

```
proc mixed;
  class treatment visit subjid;
  model change=treatment baseline visit treatment*visit baseline*visit / ddfm=kr;
  repeated visit /type=un subject=subjid;
  lsmeans treatment*visit / diff cl;
  ods output diffs=diffs lsmeans=lsmeans;
run;
```

8.2 Secondary Efficacy Analyses

The secondary endpoint analysis will be performed on the FAS.

- MADRS response rate
- MADRS remission rate
- CGI-I improvement rate

The MADRS response rate in the OPC-64005 20-mg group will be compared with that in the placebo group using the χ^2 test in the LOCF dataset. The differences in the response rates between each OPC-64005 group and the placebo group, as well as the two-sided 95% CI (Wald confidence interval), will be determined. The MADRS remission rate and CGI-I improvement rate will be analyzed in the same manner as the MADRS response rate. The same analysis will be performed on the OC dataset.

- Mean change from baseline in HAM-D 17-item total score
- Mean change from baseline in Apathy Scale score

An analysis will be performed on the mean change from baseline in HAM-D 17-item total score using the analysis of covariance (ANCOVA) model with treatment group as a factor and baseline as a covariate in the LOCF dataset. The least square means of each treatment group and the difference in the least square means between each OPC-64005 group and the placebo group, as well as the two-sided 95% CIs, will be calculated. The mean change from baseline in Apathy Scale total score will be analyzed in the same manner as the mean change from baseline in HAM-D 17-item total score. The same analysis will be performed on the OC dataset.

- Mean change from baseline in CGI-S
- Mean change from baseline in MADRS-S total score (total score of Items 1 through 9)
- Mean change from baseline in MADRS anhedonia factor score (total score of MADRS Items 1, 2, 6, 7, and 8)

The MMRM analysis will be performed in the same manner as that for the primary endpoint.

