6.3 Measures to Minimize/Avoid Bias

This trial will be performed as a randomized double-blind trial to minimize bias.

Treatment assignment codes will not be disclosed to the subjects or investigator. Except for designated persons, the treatment assignment code will not be disclosed to the sponsor's trial staff including contract research organizations (CROs) (except for the bioanalytical laboratory and pharmacogenomic [PGx] laboratory) during the trial.

Emergency keys are controlled by the IRT system until the end of the trial. They will be disclosed according to the procedures for breaking the blind when a medical emergency occurs to a subject and it is judged important to identify the treatment assignment code for treatment of the subject. Procedures for breaking the blind can be found in Section 8.8.7.

If the IMP is collected by the sponsor before unblinding, the IMP will be collected in the sealed state.

Subjects will be assigned to the OPC-64005 10-mg group, OPC-64005 20-mg group, or placebo group at a ratio of 1:4:4 using the dynamic allocation method (minimization method). A separate specification will be developed to provide details.

Results of drug concentration measurement and PGx assessment should be retained in a manner that prevents their disclosure until unblinding at the end of the trial. These tests

will be performed by the specified laboratories, and will not be performed at a clinical laboratory of the trial site.

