9.1 Sample Size

As no clinical trials of OPC-64005 in patients with MDD have been previously conducted, the target number of subjects was determined based on the results from another antidepressant clinical trial using MADRS score as the primary endpoint. In the phase 3 clinical trial of escitalopram conducted outside Japan, 1 the mean change (\pm SE) from baseline in MADRS total score at the final timepoint of Week 8 (8 weeks after start of administration) determined using last observation carried forward analysis of covariance was -9.4 ± 0.9 in the placebo group (n = 119), -12.0 ± 0.9 in the citalogram 40-mg group (n = 125), -12.8 ± 0.8 in the escitalopram 10-mg group (n = 118), and -13.9 ± 0.8 in the escitalopram 20-mg group (n = 123). Referring to those results, in the present trial it is assumed that the difference between the OPC-64005 20-mg group and the placebo group in the change from baseline in MADRS total score at Week 6 of the double-blind treatment period will be -4 with a standard deviation of 11. To ensure a power of 80% in a two-sided test with a significance level of 0.05, 120 subjects each are required for the OPC-64005 20-mg group and the placebo group. For the OPC-64005 10-mg group, the number of subjects was set at 30 without statistical consideration. The planned number of subjects to be randomized for the trial was therefore set at 270.

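### Response, remission and CGI-I improvement are compared without baseline adjustment: a valid analysis, but one that gives up a modest amount of precision

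*SAP*

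**What the plan says.** SAP 8.2 says of the first binary endpoint: "The MADRS response rate in the OPC-64005 20-mg group will be compared with that in the placebo group using the" chi-square test on LOCF data. For the rate differences, the "two-sided 95% CI (Wald confidence interval), will be determined". It continues: "The MADRS remission rate and CGI-I improvement rate will be analyzed in the same manner as the MADRS response rate". The SAP repeats the analysis on observed cases. Protocol 9.4.1.3 gives the same test and interval. No covariate or stratum is named, and neither document contains an adjusted or stratified analysis of these rates.

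The continuous endpoints are handled differently. The primary MMRM (SAP 8.1.1) carries baseline and its interaction with time. In SAP 8.2, the HAM-D and Apathy Scale ANCOVA uses baseline as a covariate, and the CGI-S, MADRS-S and anhedonia factor analyses repeat the primary MMRM. Baseline MADRS and CGI-S are summarised under SAP 7.3 and used as subgroup variables in SAP 8.3.

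**The concern.** Remission requires a MADRS total of 10 or less together with at least a halving of the baseline score (Protocol Section 3, SAP 6.2). From a baseline of 20 or more, the fixed cut at 10 decides the outcome, so a more severely ill patient has further to fall. Entry is restricted on HAM-D and MADRS-S, not on clinician-rated MADRS, so baseline MADRS is free to vary.

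Baseline score can therefore explain part of the variation in the binary outcomes, and the planned analysis leaves that part in the error. A chance difference between arms in baseline MADRS also carries into the rate difference uncorrected. What is at stake is the width of three secondary confidence intervals and a few points of power. The validity of the comparison is not in question.

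**Working it through.** **Inputs from the documents**
- Planning effect: the MADRS difference "will be -4 with a standard deviation of 11" (SAP Section 4).
- Power target, primary endpoint only: "To ensure a power of 80% in a two-sided test with a significance level of 0.05" (SAP Section 4).
- Size: "120 subjects each are required for the OPC-64005 20-mg group and the placebo group" (Protocol 9.1).
- Allocation: "at a ratio of 1:4:4 using the dynamic allocation method (minimization method"), which is 1:1 for 20 mg against placebo (Protocol 6.3).
- Placebo change: -9.4, from the escitalopram reference trial (Protocol 9.1).

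**Assumptions not in the documents**
- Baseline MADRS mean/SD of 28/4, 30/5, 30/6 or 32/6.
- Correlation of baseline with change from -0.4 to +0.1.
- CGI-I improvement represented by a proxy: a noisy version of the MADRS change, cut at -12.
- Baseline MADRS as the covariate throughout. Adjustment for CGI-S was not simulated.

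**Step 1: the plan's own figure.** n per arm = 2 x (1.960 + 0.842)^2 x 11^2 / 4^2 = 118.7, so 119 by the normal formula. The t-based version gives 119.7, so 120, with power 0.801. The stated 120 is reproduced. The documents give no power, rate or precision for the three binary endpoints.

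**Step 2: precision with and without adjustment.** Week 6 scores were simulated (1,000,000 draws per scenario) and the three outcomes derived from them. With n per arm:
- Unadjusted variance of the risk difference = [p0(1 - p0) + p1(1 - p1)] / n.
- Adjusted variance = large-sample variance of the standardised risk difference from a logistic model with treatment and baseline MADRS.
- Power = Phi(d / SE - 1.96), where d is the risk difference.

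Adjusted/unadjusted variance ratio, range over the four baseline settings:

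| Baseline-change correlation | Remission | Response | CGI-I proxy |
|---|---|---|---|
| -0.4 | 0.990-0.999 | 0.966-0.989 | 0.915-0.916 |
| -0.3 | 0.973-0.998 | 0.991-1.000 | 0.953 |
| -0.2 | 0.948-0.986 | 0.997-1.000 | 0.979-0.980 |
| -0.1 | 0.916-0.964 | 0.982-0.996 | 0.995 |
| 0.0 | 0.879-0.934 | 0.958-0.979 | 1.000 |
| +0.1 | 0.838-0.896 | 0.925-0.953 | 0.995 |

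The largest power gains are 6.6 points for remission (43.1% to 49.7%), 3.3 for response (55.6% to 58.9%) and 3.7 for CGI-I (54.5% to 58.2%). Chi-square power without adjustment is about 39-62% for remission, 53-66% for response and 52-54% for the CGI-I proxy.

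**Step 3: middle case by hand** (baseline 30/6, correlation -0.1, remission 0.197 against 0.303).
- Unadjusted SE = sqrt[(0.197 x 0.803 + 0.303 x 0.697) / 120] = 0.0555.
- Adjusted SE = 0.0555 x sqrt(0.916) = 0.0531.
- Half-width of the 95% CI: 1.96 x 0.0555 = 10.9 percentage points, against 1.96 x 0.0531 = 10.4.
- Power is 48.2% unadjusted and 51.7% adjusted (unrounded rates).
- Equivalent size: 120 / 0.916 = 131 per arm.
- In the same case, response goes from 60.2% to 60.9% and CGI-I from 54.1% to 54.3%.

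**Step 4: finite samples.** A separate simulation compared the logistic Wald test with chi-square: 3,000 trials per setting, placebo change -10, baseline mean 29, SD 4-6, baseline-to-Week-6 correlation 0.2-0.5. Adjustment changed remission power by about +1 to +6 points and response by about -1 to +3. The SE of one simulated power is at most sqrt(0.25/3000) = 0.9 points, so the small changes lie within noise.

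**Step 5: validity and imbalance.** Simulated type I error of the chi-square test is 0.046-0.057 (4,000 trials). Under simple randomisation with a baseline SD of 6, the SE of the between-arm baseline difference is 6 x sqrt(2/120) = 0.77 points, so a chance difference of about 1.5 points is plausible.

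**The case against.** The case for leaving the plan alone is respectable. The trial is exploratory, these endpoints are secondary, Protocol 9.4.1.4 places no error control on them, and no power target for them exists to be missed. Two of the three endpoints already refer to the patient's own baseline: response is a percentage reduction, and CGI-I is rated against the condition at Visit 3 (Protocol 8.1.2). The gain rests on a baseline SD and a correlation that the documents do not give. All of this stands, and it keeps the point small.

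Four stronger readings are tempting, and the documents do not support them.
- *The chi-square comparison is wrong.* It is not. The test keeps its level and the unadjusted difference estimates the intended quantity.
- *The binary endpoints are the only comparisons without baseline.* The Wilcoxon sensitivity test (SAP 8.1.2.2) and the CGI-I score comparison (SAP 8.4) also name no baseline term. The contrast holds for the continuous primary and secondary endpoint models, not for every continuous analysis.
- *Remission is always the main beneficiary.* In the table this holds in all four baseline settings at a correlation of -0.1 or higher and in three of four at -0.2. At -0.3 or more negative, CGI-I gains most and remission gains at most 2.7% of variance.
- *Baseline imbalance is left uncontrolled.* Allocation is by minimization, with its factors in a separate specification, so the reviewed text cannot show whether baseline MADRS is among them. SAP 7.3 will also tabulate baseline MADRS by arm, so an imbalance would be visible, though not corrected.

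Dropping response and CGI-I from the proposal goes too far. Large-sample precision is not worse for any endpoint in any scenario, and one method for all three is simpler to specify.

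**Conclusion.** The point holds as an optional precision improvement. All three binary endpoints are analysed without baseline although a suitable covariate is on file. Adjustment would reduce the variance of the risk difference by about 0-16% for remission, 0-8% for response and 0-9% for CGI-I improvement. In power that is 0-7 points for remission and under 4 for the other two. A fair central expectation is remission power of 48% rising to 52%, with almost no change for the others.

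These figures assume the planning effect, an SD of change of 11, 120 evaluable subjects per arm, the baseline distributions and correlations listed above, and a proxy for CGI-I. The ordering of the endpoints depends on the baseline-change correlation, which the documents cannot settle.

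**What to change.** In SAP 8.2, make the main analysis of each binary endpoint a logistic regression on treatment group and baseline:
- Covariate: MADRS total for response and remission; for CGI-I improvement, which has no baseline of its own, either baseline CGI-S or baseline MADRS, named in advance.
- Estimate: the standardised (marginal) risk difference, which keeps the planned measure and avoids a switch to a conditional odds ratio.
- Inference: a delta-method or robust 95% CI, with the p-value taken from the same estimate so that test and interval cannot disagree.
- Support: keep the chi-square test and Wald interval, and run both approaches on the LOCF and observed-case data as now planned.

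A simpler alternative is stratification on the SAP's own baseline MADRS cut of 30. In the middle case it recovers (1 - 0.942) / (1 - 0.916) = 69% of the remission gain.

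Because Protocol 9.4.1.3 also names chi-square, record the change in SAP Section 14 before data lock. The cost is a paragraph of SAP text, a few lines of code and slightly more complex reporting. Design, data collection and sample size are untouched.

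### The planned 95% Wald intervals cover only about 92–94% for 10 mg (n = 30) versus placebo, and less for rare outcomes; a score interval would bring them close to 95%

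*SAP*

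**What the plan says.** SAP 8.2 asks for "The differences in the response rates between each OPC-64005 group and the placebo group" together with a confidence interval: "as well as the two-sided 95% CI (Wald confidence interval), will be determined". The other two binary endpoints follow suit: "The MADRS remission rate and CGI-I improvement rate will be analyzed in the same manner as the MADRS response rate". The LOCF dataset is the main one, and SAP 8.2 repeats the analysis on the OC dataset. Protocol 9.4.1.3 names the same interval.

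The hypothesis test is narrower than the interval: "The MADRS response rate in the OPC-64005 20-mg group will be compared with that in the placebo group using the" chi-square statistic. No test is planned for 10 mg.

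Randomization is "at a ratio of 1:4:4 using the dynamic allocation method (minimization method"), for 10 mg, 20 mg and placebo in that order. Protocol 9.1 sizes the 20-mg and placebo groups at 120 each; for the 10-mg group, "the number of subjects was set at 30 without statistical consideration". SAP 4 repeats these sizes.

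Neither document gives a rule for zero cells, a continuity correction or an alternative interval. Neither gives an expected rate for any of the three endpoints.

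**The concern.** The Wald interval estimates each arm's variance from the observed proportion alone. In a small arm with a low event rate, that estimate is unstable and correlated with the proportion itself: few events give a low rate and a small variance at the same time. The interval then misses more often than its label says, and mostly on one side. In an arm with no events, the estimated variance is zero.

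The 10-mg arm is the only small one, and it receives this interval on three endpoints. With no 10-mg test planned, the interval is the only inferential statement about 10 mg on these endpoints. Remission is the most exposed. It requires a MADRS total of 10 or less as well as a 50% reduction (SAP 6.2), so it can never be more frequent than response.

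**Working it through.** **Inputs.** Arm sizes are 30 (10 mg), 120 (20 mg) and 120 (placebo), from Protocol 9.1 and SAP 4. The nominal level is 95%, so z = 1.96. True rates are assumptions, because the documents give none for these endpoints. The only response rate in the text is a background 50–65% for antidepressants (Protocol 2.2.1), which is not a planning value.

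**The plan's own figure.** For a difference of 4, SD 11, 80% power and two-sided 0.05, n = 2 × (1.96 + 0.842)² × 11² / 4² = 118.7, so 119 per arm by the normal approximation. The t-test gives 119.7, so 120. The stated 120 is reproduced. The plan states no coverage figure.

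**Formulas.** Let p1 = x/30 (10 mg) and p2 = y/120 (placebo).
- Wald: (p1 − p2) ± 1.96 × √[p1(1 − p1)/30 + p2(1 − p2)/120].
- Newcombe: with Wilson limits (l1, u1) and (l2, u2) for the two arms, the lower limit is (p1 − p2) − √[(p1 − l1)² + (u2 − p2)²] and the upper limit is (p1 − p2) + √[(u1 − p1)² + (p2 − l2)²].
- Coverage: sum the product of the two binomial probabilities over all 31 × 121 outcomes whose interval contains the true difference.

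**Results, 30 versus 120, equal true rates.** Coverage and misses are in %, mean widths in percentage points. A miss below means that the whole interval lies below the true difference, so 10 mg looks worse than it is.

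| True rate | Wald coverage | Wald misses below | Wald misses above | Newcombe coverage | Wald width | Newcombe width |
|---|---|---|---|---|---|---|
| 10% | 91.7 | 7.4 | 0.9 | 95.8 | 23.1 | 25.2 |
| 15% | 92.5 | 6.1 | 1.3 | 95.4 | 27.8 | 28.5 |
| 20% | 93.0 | 5.3 | 1.7 | 95.3 | 31.3 | 31.2 |
| 30% | 93.7 | 4.2 | 2.1 | 95.0 | 36.1 | 34.9 |
| 40% | 93.9 | 3.5 | 2.6 | 94.9 | 38.6 | 36.9 |
| 50% | 93.9 | 3.1 | 3.1 | 94.5 | 39.4 | 37.6 |

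- Over all pairs of rates from 15% to 65%, Wald coverage runs from 92.2% to 94.1%, mean 93.7%.
- With the 10-mg rate at 50–65% and placebo at 20–65%, it is 93.5–94.1%.
- If the OC dataset lost 20% of each arm (an assumption; 24 versus 96), Wald coverage would be 90.2% at 10% and 92.8% at 20%.
- For 20 mg versus placebo (120 versus 120), it is 94.1–95.2%, mean 94.8%, over rates of 10–60%.

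**No events in the 10-mg arm: 0/30 versus 12/120.**
- Wald: the standard error is √(0 + 0.1 × 0.9/120) = 0.0274, so −10.0 ± 5.4 points, that is −15.4 to −4.6.
- Newcombe: the Wilson limits are 0 to 11.35% and 5.81% to 16.67%. Lower: −0.10 − √(0² + 0.0667²) = −16.7 points. Upper: −0.10 + √(0.1135² + 0.0419²) = +2.1 points.

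Wald excludes zero here and Newcombe does not. The chance of 0 events in 30 is 0.9³⁰ = 4.2% at a true rate of 10%, 0.85³⁰ = 0.8% at 15% and 0.8³⁰ = 0.12% at 20%.

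**A case with events in both arms: 2/30 versus 24/120.** Wald gives −24.8 to −1.9 points and Newcombe −22.7 to +2.6. The reading can differ without an empty cell.

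**The case against.** The strongest reply is that no planned decision depends on this interval. The trial is an exploratory phase 2 study. The secondary endpoints are there to evaluate 20 mg (SAP 6.2), and the 10-mg arm was added for safety (Protocol 4.3.2). The interval is 30–40 points wide by either method at rates of about 20% or more. At the 50–65% response rates mentioned in the background, the shortfall in coverage is only about 1 point. Wald is a standard interval, stated consistently in both documents, and Amendment 1 adopted it deliberately in place of Clopper-Pearson because it suits a difference between groups. All of this stands and limits the weight of the point. It does not make the 95% label accurate at 30 subjects, and score intervals suit a difference between groups equally well.

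Three stronger readings are tempting, and the documents do not support them.
- **The interval collapses when the 10-mg arm has no events.** Only that arm's variance term vanishes; the placebo term remains. In the example above the interval is still 10.7 points wide. It becomes a single point only when both arms have no events.
- **Wald intervals are generally too short for this arm.** From about 20% upward, Newcombe is slightly narrower on average (table). There the coverage loss does not come from shorter intervals on average. Nor does Wald flatter 10 mg: at low rates its excess misses run against 10 mg.
- **Coverage is as low as 81%.** That needs a true rate of 5% in both arms (81.1%), which nothing in the documents suggests.

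**Conclusion.** The point holds, with modest weight. For 10 mg versus placebo the nominal 95% Wald interval covers about 92–94% if true rates lie between 15% and 65%, and 91.7% if both are 10%. At low rates the misses fall mostly on the side that makes 10 mg look worse than it is. With no events in the 10-mg arm, the interval is too narrow and can exclude zero when it should not.

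The size rests on assumed rates and on arms of 30 and 120; a smaller analysis set would do slightly worse. Newcombe gives about 94.5–95.8% at the rates in the table. The primary analysis, the chi-square tests and, in practice, the 20-mg intervals are not affected.

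**What to change.** In SAP 8.2 and Protocol 9.4.1.3, replace the Wald interval with the Newcombe (Wilson score) or the Miettinen-Nurminen interval for the differences in response, remission and CGI-I improvement rates. Name one of the two, and apply it to both dose groups in the LOCF and OC datasets. The coverage figures above are for Newcombe; Miettinen-Nurminen was not enumerated here. Leave the chi-square test unchanged. Make the change before unblinding.

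The cost is one software option and a short text change, with no new data. The 10-mg limits shift slightly; for example, 6/30 versus 24/120 moves from −16.0 to +16.0 points to −13.2 to +18.4. The 20-mg interval barely changes: 36/120 versus 24/120 moves from −0.9 to +20.9 points to −1.0 to +20.7. Using one method for both doses is simpler than treating 10 mg separately, and costs nothing for 20 mg.
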